### Sensitivity analyses of the primary endpoint

The following sensitivity analyses will be made

- To assess the impact of the endpoints calculated from MMTT that is stopped before 4 hours due to hyperglycaemia or hypoglycaemia, a sensitivity analysis will be performed excluding these endpoints.

- To assess the impact of the endpoints calculated from MMTT profile that includes imputed values, a sensitivity analysis will be performed excluding these endpoints.
- A sensitivity analysis will be performed excluding endpoints calculated from the MMTT, where the date of the MMTT is more than one day after the last liraglutide dosing.
- An analysis using last observation carried forward (LOCF) of the primary endpoint. The analysis will be made using a normal linear regression model for the log-transformed primary endpoint with treatment, stratum and sex as fixed factors and age and baseline value (log-transformed) as covariates.
- An analysis based on the subjects completing the treatment period (i.e. completing the visit at week 54). The analysis will be made using a normal linear regression model for the log-transformed primary endpoint with treatment, stratum and sex as fixed factors and age and baseline value (log-transformed) as covariates
- In case the assumption of equal variance-covariance between the treatments turns out not to be reasonable a sensitivity analysis will be added where the variance-covariance matrix for the repeated measurements for each subject will depend on treatment.

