Due to the nature of the development of T1DM and the progressive decline in beta-cell function and non-fasting C-peptide over time, only a randomised parallel-group design will make comparison to the natural course of the disease development (placebo) possible during the administration period.

There is currently no approved comparator available for beta-cell function preservation after onset of T1DM. Thus placebo is the relevant comparator.

CONFIDENTIAL

Date: Version: Status: Page: 07 May 2015 **Novo Nordisk** 2.0 Final 40 of 141

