# 6 Trial population

# 6.1 Number of subjects

Number of subjects planned to be screened: 600

Number of subjects planned to be randomised: 304

Maximum number of subjects to be randomised: 314

Number of subjects expected to complete the trial (defined as reaching primary endpoint): 240

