## 2.1 Sample size calculation

This is a phase 2 trial and the first Novo Nordisk trial of NNC0114-0006 in subjects with newly diagnosed T1DM. Therefore the knowledge on treatment effects and on the standard deviation of the primary endpoint is limited.

The statistical power calculations have been done under the following assumptions

- The primary endpoint is  $AUC_{0-4h}$  for a MMTT stimulated C-peptide concentration-time curve at week 54 relative to baseline, i.e.  $AUC_{0-4h, C-peptide, 54w} / AUC_{0-4h, C-peptide, baseline}$ . The primary endpoint will be log-transformed in the statistical analysis and this will be denoted  $\ln(AUC_{0-4h, C-peptide, \Delta 54w})$ . Thus,  $AUC_{0-4h, C-peptide, \Delta 54w}$  is the proportion of  $AUC_{C-peptide}$  that is preserved after 54 weeks relative to the level at baseline. E.g. a reduction of  $AUC_{C-peptide}$  of 35% corresponds to a preservation of 65% and value of the  $\ln(AUC_{0-4h, C-peptide, \Delta 54w})$  is  $\ln(0.65) = -0.431$ .
- The residual standard deviation of  $\ln(AUC_{0-4h, C-peptide, \Delta 54w})$  in the model described above may depend on the treatment. Based on the results of Herold et al. the standard deviation is assumed to be 1 in the placebo group and 0.5 in the group treated with NNC0114-0006 in combination with liraglutide.
- The expected preservation in the placebo treated patients is 65%, based on the results of Herold et al. who found a mean of 70% decline in  $AUC_{C-peptide}$  over a 24-months period. Assuming a linear decline, the mean 12-months decline would be 35%, i.e. a preservation of 65%. The statistical power calculations have been done assuming three levels of treatment effects for NNC0114-0006 in combination with liraglutide; a preservation of 85% and 95% and 98%, respectively.

[Table 2-1](#) shows the statistical power for the test of no treatment effect if the true mean preservation is 85%, 95% or 98% in the group treated with NNC0114-0006 in combination with liraglutide and 65% in the placebo group when the numbers of completers are 40, 60 or 80, respectively using a two-sided test and 5% level of significance. The rows corresponding to the chosen number of (completing) subjects are highlighted.

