**Table 2–1 Power calculations**

True treatment effect (preservation)	N (completers per group)	Statistical power
85%	40	0.320
85%	60	0.451
85%	80	0.566
95%	40	0.561
95%	60	0.740
95%	80	0.854
98%	40	0.628
98%	60	0.804
98%	80	0.903

Assuming a preservation of 98% and a SD of 0.5 for NNC0114-0006 in combination with liraglutide and a preservation of 65% and a SD of 1 for placebo, then the power will be 80.4% with 60 subjects completing the trial in each of the two treatment arms.

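### With about 21% dropout implied by the plan, no stated sensitivity analysis of the week-54 primary endpoint tests loss of accrued benefit after stopping treatment

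*SAP*

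**What the plan says.** The primary analysis (SAP section 2.3) is an MMRM on the log of the C-peptide AUC ratio, using the available assessments at weeks 12, 24, 36 and 54. The SAP then lists six sensitivity analyses. Two deal with subjects who have no week-54 value: "An analysis using last observation carried forward (LOCF) of the primary endpoint" and "An analysis based on the subjects completing the treatment period (i.e. completing the visit at week 54"). Both are linear regressions with treatment, stratum, sex, age and log baseline.

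The other four serve different purposes. Three drop certain meal-test results: tests stopped early for hyper- or hypoglycaemia, profiles with imputed values, and tests more than one day after the last liraglutide dose. The fourth is conditional and lets the covariance matrix differ by treatment. None is reference-based, delta-adjusted or a tipping-point analysis. Where SAP section 2.3 calls carrying forward conservative, it means filling in the rest of a single stopped meal test, not handling dropout.

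On the amount of missing data, Protocol section 6.1 plans 304 randomised and states: "Number of subjects expected to complete the trial (defined as reaching primary endpoint): 240". Under Protocol section 8.1.7, subjects withdrawn during treatment get Visit 63-type procedures promptly and a later safety visit. No meal test is scheduled for them at week 54.

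**The concern.** Protocol section 5.5 refers to "the progressive decline in beta-cell function and non-fasting C-peptide over time". With such an endpoint, a carried-forward ratio holds a dropout at an earlier, higher level, so LOCF favours whichever arm loses more subjects. It also treats carried values as observed, so its standard error ignores the imputation. The completer analysis and the MMRM both let dropouts take the course of those who stayed.

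The case in which a subject stops and then gives back what was gained is therefore not examined. The documents make it plausible. Protocol section 3.2 says, of earlier immunosuppressive treatments, that the disease tends to return once treatment stops. Several mandatory withdrawal criteria in Protocol section 6.6 relate to tolerability, missed infusions, infection or glycaemic problems, so dropout may differ by arm. If it does, the planned checks could agree with each other and still overstate the effect in all randomised subjects, which is what the ITT principle in SAP section 2.2 points to.

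**Working it through.** **Inputs from the documents**

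- Test: "using a two-sided test and 5% level of significance" (SAP 2.1).
- Placebo: "The expected preservation in the placebo treated patients is 65"% (SAP 2.1).
- Combination: "Assuming a preservation of 98% and a SD of 0.5 for NNC0114-0006 in combination with liraglutide" (under SAP Table 2-1).
- Log-scale SDs: "the standard deviation is assumed to be 1 in the placebo group and 0.5 in the group treated with NNC0114-0006" in combination with liraglutide (SAP 2.1).
- 304 randomised 1:1:1:1, so 76 per arm; 240 reaching the endpoint, so 60 per arm.

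**Assumptions, not in the documents:** equal dropout unless stated; last meal test at week 12, 24 or 36 in equal shares; log-linear decline unless stated.

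1. *The plan's own power.* Effect = ln(0.98/0.65) = 0.4106, ratio 1.51. SE = √(0.5²/60 + 1²/60) = 0.1443. Power is 0.812 by the normal approximation and 0.803 by Satterthwaite t, against the stated 0.804. All nine cells of Table 2-1 reproduce within 0.002 by Satterthwaite t.

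2. *Dropout.* 1 − 240/304 = 21.05%. Also 60/(1 − 0.2105) = 76 per arm and 4 × 76 = 304, so this rate matches the sample size.

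3. *Full loss of benefit.* If 21.05% of the combination arm end at the placebo mean, the effect is 0.4106 × 0.7895 = 0.3241, ratio exp(0.3241) = 1.38. z = 0.3241/0.1443 = 2.25. Power is 0.61 with the SE for 60 per arm, or 0.715 with the SE for 76 per arm (0.1282). For 10% to 35% combination dropout the ratio runs from 1.45 to 1.31, and power (SE for 60) from 0.73 to 0.46. If true preservation is 95% or 85%, power at 21% dropout is 0.55 or 0.31, against 0.74 or 0.45 in Table 2-1.

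4. *LOCF with equal dropout.* LOCF keeps the between-arm difference at the last visit, on average 24/54 of the final one. Effect = 0.4106 × (1 − 0.2105 × 30/54) = 0.3626, ratio 1.44. If the decline is linear on the original scale the ratio is 1.43. Both lie between 1.51 and 1.38.

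5. *LOCF with unequal dropout and no drug effect.* The upward offset for a dropout at week w is −ln(0.65) × (1 − w/54): 0.34, 0.24 and 0.14 at weeks 12, 24 and 36, mean 0.239. With an assumed 30% vs 12% split the false ratio is exp(0.18 × 0.239) = 1.04 (1.05 with linear decline). With 35% vs 10% it is exp(0.25 × 0.239) = 1.06.

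6. *Would the planned analyses notice?* In 4,000 simulated trials (76 per arm, 21% random dropout, linear decline, combination dropouts losing all benefit), the true ratio was 1.38. Completers gave 1.50 and LOCF 1.43, practically the same as when no benefit was lost (1.51 and 1.43).

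7. *Tipping point.* At the design effect, significance is lost when (0.4106 − 1.988 × 0.1443)/0.2105 = 0.59. Combination dropouts would have to average 0.59 log units below combination completers: 0.98 × exp(−0.59), about 54% preservation.

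**The case against.** A reader might infer that MMRM, LOCF and completers share one optimistic assumption, namely that the full effect survives dropout. The documents do not support that for LOCF. It keeps only the difference reached at the last visit, and with equal dropout and timing its expected effect equals that of copy-increments. Under those conditions the plan already has a point estimate for no further benefit. What it lacks is a test of losing benefit already gained, and the LOCF estimate still depends on equal dropout and comes with an unsuitable standard error.

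A reader might also infer that LOCF must favour active treatment. The documents give no dropout rates by arm. Intolerance could raise active-arm dropout, but withdrawal for hyperglycaemia with ketosis could raise placebo dropout if the drugs work, and LOCF would then count against them. The 1.04 to 1.06 rests on assumed splits, and a log bias of 0.043 is about 0.3 of the design SE.

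Three further points have weight:

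- Visit 63 procedures include the meal test, so the carried value may come from the withdrawal visit, and the offsets in step 5 may be too large. The SAP does not say how that visit is used.
- The week-80 endpoint gives direct evidence on persistence off treatment, but it is not an analysis of missing week-54 values.
- This is a phase 2 proof-of-principle trial, and SAP sections 2 and 2.2 allow additional analyses. None for this purpose is pre-specified.

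Return to the placebo mean is also an extreme case for someone who stops late, and is best read as a bound.

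**Conclusion.** The gap is real, but narrower than it may first appear. The stated sensitivity analyses for a missing week-54 value do not cover loss of accrued benefit, while the plan's own numbers imply that about one subject in five will lack that value. At the design effect, full return to placebo among 21% of combination subjects lowers the ratio from about 1.51 to about 1.38, and LOCF or completers would not show it.

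A reader might infer that the trial's conclusion would reverse. The figures do not support this: z stays at about 2.2 in expectation, and dropouts would have to fall below the assumed placebo level before significance is lost. The margin is thinner if the true effect is smaller than the design case. The consequence is a possibly overstated effect and untested robustness in a sensitivity set; the choice of MMRM as primary is not in question. The sizes rest on the assumed dropout split, timing and decline shape. The absence of a loss-of-benefit analysis does not.

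**What to change.** Keep the MMRM as primary. In SAP section 2.3, replace the LOCF sensitivity analysis with placebo-reference multiple imputation of ln(AUC ratio) at week 54, using the same covariates and Rubin's rules. Use jump-to-reference as the loss-of-benefit bound and copy-increments as the intermediate case. State how meal tests from early-withdrawal visits enter each analysis: as week 54, as the nearest scheduled visit, or not at all. The exploratory liraglutide-concentration analysis in SAP section 2.3 is built on the LOCF model, so its base model needs to be restated.

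This is a cheap improvement: SAP text and one standard program, with no new data and no change to trial conduct. The downside is some extra programming and a more conservative sensitivity estimate. SAP section 3 already lists changes to the sensitivity analyses made before the code break. This change belongs with them, or should be labelled post hoc if made later.

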## **Exploratory analyses**

### ***Effect of stratum on the primary endpoint***

An exploratory analysis will be made to investigate a potential interaction between treatment and stratum for the primary endpoint. The analysis will be made by adding the interaction between stratum, treatment and visit as a factor in the mixed model for repeated measurements (MMRM) described for the primary endpoint. The treatment means and the treatment ratios at selected time points including week 54 will be presented with 95% CIs for each stratum separately.

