## Figure 5–1 Trial design

## 5.2 Rationale for trial design

The rationale for the trial design, is to investigate the effect of NNC0114-0006 and liraglutide in combination on preservation of beta-cell function compared to placebo at week 54 in adult subjects with newly diagnosed T1DM with residual beta-cell function. In addition to the effect of the combination of NNC0114-0006 and liraglutide on preservation of beta-cell function, the trial will also generate data of treatment with either NNC0114-0006 or liraglutide compared to placebo on preservation of beta-cell function. The duration of the trial with 54 weeks of exposure of NNC0114-0006 and/or liraglutide has been chosen to align with the regulatory requirements from FDA and EMA. The length of the observation period of 26 weeks is chosen to give guidance for the further development program for the combination therapy of NNC0114-0006 and liraglutide. The FDA and
Protocol Trial ID: NN9828-4150 UTN: U1111-1154-7172 EudraCT no.: 2014-001215-39	NFIDENTIAL	Date: 07 Version: Status: Page:	7 May 2015 Novo Nordis 2.0 Final 35 of 141	k
--	------------	--	---	---

EMA guidelines advice that studies of products aimed at preservation of beta-cell function in recent-onset T1DM with remaining endogenous insulin reserve, should evaluate metabolic outcomes, such as stimulated C-peptide levels. Therefore the MMTT stimulated  $AUC_{0-4h}$  C-peptide concentration has been chosen as the primary efficacy parameter.

The randomisation will be stratified according to non-fasting C-peptide level. The stratification factor has two levels according to C-peptide value:  $\geq 0.2 \text{ nmol/l to } \leq 0.6 \text{ nmol/l and } > 0.6 \text{ nmol/l}$ . There is no cap on the size of the strata. The effects of NNC0114-0006 on preservation of beta-cell function may depend on the level of the residual beta-cell function. The fasting C-peptide level is a marker of the residual beta-cell function and by stratifying for non-fasting C-peptide, the treatment arms are balanced with regards to the residual beta-cell function.

Clinical meaningful endpoints have been included such as number of treatment emergent hypoglycaemic episodes, insulin injections per day, and change in HbA1c. Furthermore, other secondary end-points e.g. total insulin usage and fasting values of glucose, insulin, glucagon and C-peptide have been included to describe effect of treatments on the glucose metabolism and insulin usage.

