# 17 Statistical considerations

If necessary, a statistical analysis plan (SAP) may be written in addition to the protocol, including a more technical and detailed elaboration of the statistical analyses. The SAP will be finalised before database lock.

Based on the statistical model, treatment means or geometric means (LSMeans) and treatment comparisons (i.e. treatment differences or treatment ratios) will be presented with 95% confidence intervals (CI) and p-values for the two-sided test of no treatment difference. A significance level of 5% will be used. All pairwise treatment differences (or ratios) will be presented. No adjustment for multiple testing will be performed.

Some endpoints will be summarised for the treatment period, for the observation period and for the entire trial period (i.e. the treatment period together with the observation period)

The treatment period and the observation period will be derived for completed subjects as

- The start of the treatment period will be the date of first trial product administration
- The end of the treatment period will be the day before the visit at week 54 (i.e. the day before visit 63)
- The start of the observation period will be the day after the end of the treatment period
- The end of the observation period will be the date of the last visit

For withdrawn subjects the date of last contact will be the maximum of the date of the last visit and the withdrawal date. The treatment period and the observation period will be derived for withdrawn subjects as

- The start of the treatment period will be defined as described for completed subjects
- The end of the treatment period will be as defined for competed subjects if this date is before or on the date of last contact. Otherwise the end of the treatment period will be the date of last contact
- An observation period will only be defined if the date of last contact is after the end of the treatment period
  - The start of the observation period will be defined as for completed subjects
  - The end of the observation period will be the date of last contact

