#### 2.11 Section 6.2 Inclusion criteria

2. Type 1 diabetes mellitus (as diagnosed clinically\*)  $\leq 2012$ -weeks prior to randomisation *screening* (see Section 8.2.6).

4. Non-fasting *peak*\*\* C-peptide ≥0.2 nmol/l *during MMTT at Visit 2* 

\*See Section 6.8 for the clinical diagnosis.

\*\*The highest C-peptide value of the 11 samples performed during the MMTT.

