### ***Effect of biomarkers on the primary endpoint***

The effect of the biomarkers at baseline and high resolution HLA (class I) genotyping on the primary endpoint will be explored one variable at a time.

For continuous variables, the analysis will be made by adding the biomarker at baseline (log-transformed) as a fixed effect covariate with a coefficient that depends on visit and treatment to the MMRM described for the primary endpoint. The estimated effect of the variable at selected time points including week 54 will be presented with a 95% CI for each treatment.

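### Dependence of the effect on residual beta-cell function is examined only on a two-level split at 0.6 nmol/l, although continuous baseline AUC is already in the model and could be crossed with treatment

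*SAP*

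**What the plan says.** Protocol 5.2 gives the scientific reason to look for effect modification: "The effects of NNC0114-0006 on preservation of beta-cell function may depend on the level of the residual beta-cell function". It places no cap on stratum sizes.

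SAP 2.3, *Effect of stratum on the primary endpoint*, is the only analysis of this question: "The analysis will be made by adding the interaction between stratum, treatment and visit as a factor in the mixed model for repeated measurements". Treatment means and ratios with 95% CIs are to be shown per stratum. No interaction test is named.

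SAP Table 2-2 defines the stratum by the peak C-peptide of the Visit 2 MMTT, 0.2-0.6 against above 0.6 nmol/l. Protocol Table 17-2 had the same cut on a non-fasting screening value. Amendment 2 (sections 2.1 and 2.11) moved the measure to the Visit 2 peak, defined as "The highest C-peptide value of the 11 samples performed during the MMTT". The cut was not changed, and no reason for keeping it is given.

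In the same Table 2-2, ln(baseline AUC0-4h) is a covariate whose coefficient may differ by visit but not by treatment. For continuous baseline biomarkers, the next subsection of SAP 2.3 adds the log-transformed marker "with a coefficient that depends on visit and treatment". The biomarker endpoints listed in SAP 1.1.2.2 (immune phenotyping, total IL-21, autoantibodies, with vitamin D in the same list) do not include C-peptide.

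**The concern.** The one baseline modifier that the protocol names gets the coarser analysis, while other continuous markers get a treatment-dependent slope. The better-suited variable is available. Baseline AUC is measured continuously, is defined from the Visit 2 MMTT throughout the documents, and is already in the model.

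A two-level split treats all subjects on one side of the cut as alike. If the effect changes gradually with residual function, that discards information, and more of it as the split becomes more uneven. An uneven split also leaves an imprecise estimate in the smaller stratum.

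SAP 2.4.2 says the week-54 analysis is to inform future trials. Whether benefit varies with residual function bears on eligibility and stratification there, so an analysis that could miss a real gradient has some cost.

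**Working it through.** **Inputs from the documents.** Two-sided 5% level (Protocol 17; SAP 2.1). SAP 2.1 on the log ratio: "the standard deviation is assumed to be 1 in the placebo group and 0.5 in the group treated with NNC0114-0006" combined with liraglutide. Preservation 65% on placebo and 98% on the combination in the headline case. 240 completers over four equal arms (Protocol 6.1 and 11), so 60 per arm and 120 in a pairwise comparison. The share of subjects above 0.6 nmol/l is not given; splits from 50/50 to 90/10 are **assumed**.

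**Step 1: reproduce the plan's power.** The log effect is ln(0.98/0.65) = 0.411 and its standard error is √((1² + 0.5²)/60) = 0.144. The normal approximation gives 81.2%. The noncentral t gives 80.5% (pooled degrees of freedom) or 80.3% (Satterthwaite), against 80.4% in SAP Table 2-1. The inputs are read correctly.

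**Step 2: information kept by a split.** Take a normal marker X, a treatment effect that changes linearly with X, and D the indicator of being above the cut. The share of interaction information kept is corr(X, D)² = φ(z_q)² / (q(1−q)), where q is the share in the larger stratum.

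- q = 0.5: 0.3989² / 0.25 = 0.637
- q = 0.8: 0.2800² / 0.16 = 0.490
- q = 0.9: 0.1755² / 0.09 = 0.342

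**Step 3: consequence for a pairwise comparison.** For an interaction that the continuous term detects with 80% power, the split has power Φ(2.802·√kept − 1.960), where 2.802 = 1.960 + 0.842. The effective number of completers is 120 × kept.

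| Larger stratum | Kept | Lost | Power on the split | 120 count as |
|---|---|---|---|---|
| 50% | 0.637 | 36% | 61% | 76 |
| 60% | 0.622 | 38% | 60% | 75 |
| 70% | 0.576 | 42% | 57% | 69 |
| 80% | 0.490 | 51% | 50% | 59 |
| 90% | 0.342 | 66% | 37% | 41 |

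A single-time-point simulation with 60 per arm, with main effects of both X and D in the model, kept 62%, 56%, 49% and 31% at 50/50, 70/30, 80/20 and 90/10.

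**Step 4: sensitivity to the assumptions.**

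- Log-normal C-peptide truncated at 0.2 nmol/l, assumed median 0.4 to 1.0 and log-SD 0.4 to 0.7: loss 33% to 66%. With an assumed median of 1.2 it reaches 80%.
- Normal marker split 95/5: loss 78%. Uniform marker split at its median: loss 25%.
- Gradient in ln(AUC), with a correlation between peak and AUC assumed to be 0.9 rather than 1: loss 48% at 50/50, 60% at 80/20 and 72% at 90/10.
- True modification a step exactly at the cut: nothing is lost, and the split is the better test (simulated power 77% against 58% for the continuous term at 50/50).

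**Step 5: how large a gradient is detectable.** The gradient behind the 80% figure is 2.802 × 0.144 = 0.404 on the log ratio per SD of ln(baseline). That is about as large as the whole assumed treatment effect of 0.411.

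**The case against.** Examining the interaction with the randomisation factor is conventional, and the protocol says only that the effect may depend on the level of residual function. It does not claim a linear gradient, so the continuous term carries its own assumption; with a step at 0.6 nmol/l the planned analysis is the stronger one. This stands, and it is why the by-stratum analysis should be kept.

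An interaction is likely to be underpowered with either coding. SAP Table 2-1 gives 45.1% power even for the main effect at 85% preservation, and Step 5 shows that only a very large gradient would be found reliably. This also stands and limits the practical gain.

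SAP 2 lets analyses be supplemented, and Protocol 17.6 foresees modelling of MMTT C-peptide, outside the clinical trial report. Both permit the analysis, but neither pre-specifies it. The sponsor is unblinded at the additional lock after Visit 63 (SAP 2.4.2), so a gradient model added later would be post hoc.

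A reader might infer that the low stratum can only shrink under the new measure, because a peak is never below any of its samples. The documents do not support that. The Visit 1 sample was taken on another day and is not one of the 11. Amendment 2 also moved the diagnosis window from 12 weeks before randomisation to 20 weeks before screening, and admitted subjects who would have failed the C-peptide floor at Visit 1. Both could enlarge the low stratum. What remains is a tendency: Amendment 2 itself notes that some Visit 1 values were low because subjects were fasting.

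**Conclusion.** The gap holds as a refinement of an exploratory analysis. The plan examines the modifier named in the protocol only on a two-level split. It kept the 0.6 nmol/l cut through a change of measure that would tend to put more subjects in the upper stratum. It does not cross the continuous baseline value with treatment, although it does this for other continuous markers.

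The loss is conditional: about 36% of the interaction information at 50/50, 51% at 80/20 and 66% at 90/10. These figures assume a gradient linear in log C-peptide, a roughly normal log C-peptide, and peak and AUC ranking subjects alike. None of these is in the documents, nor is the split. A reader might take a loss of a third to two thirds as a fact about this trial. It is not: Step 4 gives values outside that range, and a step at the cut would lose nothing. The primary comparison and the sample size are unaffected.

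**What to change.** Before the interim database lock, add to SAP 2.3 an exploratory analysis beside *Effect of stratum on the primary endpoint*:

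- Add treatment × visit × ln(AUC0-4h, baseline) to the primary MMRM, as a model separate from the stratum interaction.
- Report the interaction test, and the week-54 treatment ratios with 95% CIs at the 25th, 50th and 75th percentiles of baseline AUC.
- Keep the by-stratum means and ratios, and add the number of subjects per stratum and arm.

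Showing both codings covers a gradual change and a step. The cost is a short SAP paragraph and one model term. No new data are needed, and the primary analysis does not change.
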